1 INTRODUCTION

This Statistical Analysis Plan (SAP) describes the planned analysis for Mallinckrodt Pharmaceuticals protocol MNK01053115 (A Multicenter, Open-label, Study of StrataGraft Skin Tissue in Adult Subjects with Deep Partial-thickness (DPT) Thermal Burns; the StrataCAT Study). This phase 3b study is being completed to assess safety, clinical outcomes, and healthcare resource utilization (HCRU) for a single application of StrataGraft in the post excision treatment of thermally induced DPT burn that contain intact dermal elements in an adult patient population.

The following documents were reviewed in preparation of this SAP:

- Protocol MNK01053115, issued on 26 August 2019. [Amendment 1, V2, 02 October 2020]
- Case report form (CRF), issued on 20 August 2021
- ICH (E9) Guidance on Statistical Principles for Clinical Trials.

The purpose of the SAP is to ensure the credibility of the study results by pre-specifying the statistical approaches for the study analysis prior to database lock. The analyses outlined in this SAP supports the completion of the Clinical Study Report (CSR) and may be included in regulatory submissions and/or future manuscripts. Unplanned, exploratory analyses performed to support the clinical development program may not necessarily be identified in the SAP and will be identified in the CSR.

2 PROTOCOL SUMMARY

2.1 Study Design

This is a prospective, open-label, single-arm study assessing the safety and clinical outcomes of StrataGraft in the treatment of DPT thermal burn injuries with intact dermal elements. Study enrollment will be approximately 100 subjects but will continue until StrataGraft becomes commercially available or until the Sponsor decides to close the study. Enrollment will include subjects with a minimum of 3% and up to 50% TBSA of partial +/- full thickness thermal burn. Treatment will include a single application of up to 1:1 meshed StrataGraft on prepared DPT wound(s) totaling no more than approximately 2000 square centimeters in area (no more than 3 study treatment thermal burn areas and no more than 20 StrataGraft constructs applied per subject). The wound bed must be clean, excised and have bleeding controlled prior to StrataGraft application. The constructs may be anchored with tissue adhesive, staples, or sutures, and then covered with a nonadherent, nonocclusive contact layer and additional secondary dressings per institutional standard of care (dressings should not contain silver). Safety assessments will include monitoring of treatment emergent adverse events (TEAEs), serious adverse events (SAEs), wound infections, and clinically significant changes in vital signs, laboratory test results, and

immunological changes. Wound assessments will include measurements for average depth, length, and width for calculations of area and percent epithelialization. Wound assessments will be facilitated by photographs taken by the subject and/or taken by the clinical study site staff at study visits throughout the study. Scar evaluation will be conducted using the Patient and Observer Scar Assessment Scale (POSAS). Additionally, HCRU data will be collected. All eligible subjects were provided the opportunity to consent to be part of a contact database and follow-up registry; subjects will have the choice to decline with no impact to their participation in the StrataCAT study. In addition, a subset of 10 subjects (sourced from across all the sites) with closed wounds will be separately consented to have a punch biopsy (measuring 3 mm) taken from the center of the healed burn wound, and another punch biopsy measuring 3 mm taken from non-burned healthy skin. A histological evaluation of both samples will be done to analyze and contrast the skin architecture in the healed burn wound with healthy skin. The biopsy will happen at the Week 12, regardless of when wound closure occurs.

Table 1: Schedule of Assessments

Procedure	Screening +/-14 days	Day 1 Baseline	Week 1 ^a ± 2 days	Week 2 ^a ± 2 days	Week 4 ^a ± 3 days	Week 8 ^b ± 3 days	Week 12 ^b ± 7 days	Week 24 ^b ± 7 days	Visit for Confirmation of Healing ^c
Informed consent for study treatment	✓								
Consent for direct contact by Sponsor and safety registry post study ^d		✓	---	---	---	✓	---	---	---
Medical history, physical examination, and height and weight	✓								
Pregnancy test	✓								-
Vital signs	✓	✓	✓	✓	✓	✓	✓	✓	✓
Infection assessment	✓	✓	✓	✓	✓	✓	✓	✓	✓
Concomitant medications/procedures	✓	✓	✓	✓	✓	✓	✓	✓	✓
Prescription drugs given at discharge from the hospital for wound-related events including pain control, itch, psychotropics, and antibiotics		✓	✓	✓	✓	✓	✓	✓	✓
Safety laboratory tests ^e		✓ ^f					✓		
Archival plasma and leukocyte collection		✓							

CONFIDENTIAL AND PROPRIETARY

Procedure	Screening +/-14 days	Day 1 Baseline	Week 1 ^a ± 2 days	Week 2 ^a ± 2 days	Week 4 ^a ± 3 days	Week 8 ^b ± 3 days	Week 12 ^b ± 7 days	Week 24 ^b ± 7 days	Visit for Confirmation of Healing ^c
Blood collection for PRA testing (HLA I and II)		✓			✓		✓		
StrataGraft application		✓							
AE ^g /SAE /TEAE assessment	✓	✓	✓	✓	✓	✓	✓	✓	✓
Photograph of treatment sites ^h	✓	✓	✓	✓	✓	✓	✓	✓	✓
Assessment of wound closure/continued closure			✓	✓	✓	✓	✓	✓	✓
Skin quality outcome of treatment sites							✓	✓	
HCRU Assessments	✓	✓	✓	✓	✓	✓	✓	✓	✓
Biopsies ⁱ							✓		

^aIn public state of emergency situations, the Weeks 1 and 2 visit windows can be expanded to include ± 5 days.

^bIn public state of emergency situations, the Week 4 visit window can be expanded to include ± 12 days.

^bIn public state of emergency situations, the Weeks 8, 12, and 24 visit windows can be expanded to include ± 14 days.

^cThis visit may be scheduled at any time during the study to occur at least 2 weeks after initial observation of complete wound closure.

^dConsent for post study registry can be obtained at any study visit beginning at Screening (together with the consent for the study treatment), during the study treatment, or at the final study visit.

^eAny testing abstracted from the medical record from the time of admission throughout the study treatment period.

^fMay be performed within 48 hours of surgery.

^gAEs will be assessed on an ongoing basis; AEs (serious and non-serious) occurring from time of signing informed consent until completion of the Final Visit and follow-up until resolution of any ongoing TEAE at the time of study treatment completion or subject withdrawal.

^hA weekly photo taken by subject (or designate) of the treatment site(s) for the first 12 weeks and then every other week to Week 24. Photos submitted during a week when there's no in-person visit would serve as an allowable proxy for observing wound characteristics. If a subject's wound is noted to be closed for the first time via a submitted photo that should prompt a confirmation of wound healing visit 2 weeks later.

ⁱBiopsies of a closed wound and of the normal skin will be taken from a subgroup of 10 subjects.

2.2 Study Objectives and Endpoints

2.2.1 Primary Objective

The primary objective of this study is to assess the safety of a single application of StrataGraft in the treatment of adults with thermally induced DPT burns that contain intact dermal elements.

2.2.2 Other Objectives

Demonstrate the clinical outcomes of a single application of StrataGraft in the post excision treatment of thermally induced DPT burns that contain intact dermal elements.

2.2.3 Exploratory Objective

Assess for healthcare resource utilization (HCRU) throughout the study period.

2.2.4 Modification from the Statistical Section of the Final Protocol

No major modification from the latest protocol is made.

2.3 Sample Size Considerations

No sample size determination was made for this study, as this is a single treatment group, non-randomized study designed to accumulate supplemental safety and outcome data for the use of StrataGraft for the treatment of DPT wounds with intact dermal elements. This study will enroll approximately 100 subjects from up to 18 clinical study centers that previously participated in the phase 3 STRATA2016 study.

2.4 Randomization and Blinding

This study is designed as an open-label, single arm study. No randomization will be conducted, and no blinding is required for the study.

2.5 Interim Analysis (IA)

No statistical interim analyses for efficacy are planned for this study.

3 STATISTICAL METHODS AND CONVENTIONS

3.1 General Conventions

- Unless otherwise noted, the number of subjects (N), mean, standard deviation, median, minimum, and maximum will be presented for continuous variables and frequency and percentage of subjects in each category will be presented for discrete variables.
- Unless otherwise noted, confidence intervals (CIs) will be 2-sided 95% CIs.
- Listings will be sorted by subject identification, and date of the procedure or event.
- Statistical analyses will be done using Statistical Analysis Software (SAS[®]) version 9.4 or higher.
- The Kaplan-Meier estimate will be computed to determine the median time to first confirmed complete wound closure without autograft placement (date of closure is the date of the first observation of complete epithelialization without use of an autograft and confirmed with a second observation of complete closure at least 2 weeks after the first.). The 95% CI will be constructed with a generalized Brookmeyer and Crowley method.
- The Proportion and 95% CI of subjects will be calculated using the normal approximation to the binomial distribution.
- Listing will be provided for all related summary tables.

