4.3. Summary of Relevant Clinical Studies

Previous studies in adults with DPT thermal burns have demonstrated that StrataGraft skin tissue is generally safe with salutary clinical outcomes in regard to closure of DPT burns and elimination of autograft placement in the majority of subjects.

The Phase 1b study, "Open-label, Controlled, Randomized, Multicenter, Dose Escalation Study Evaluating the Safety and Efficacy of StrataGraft® Skin Tissue in Promoting the Healing of the Deep Partial-Thickness Component of Complex Skin Defects as an Alternative to Autografting," (STRATA2011) was an open-label, dose-escalation, multicenter study evaluating the safety, tolerability, and efficacy of StrataGraft skin tissue in promoting the healing of complex skin defects containing intact dermal elements. In this study, StrataGraft skin tissue was applied once to DPT burns to assess autologous tissue regeneration with reduction or elimination of

Protocol MNK01053115

StrataGraft

Amendment 1

autografts. This study included subjects with thermal burns of 3 to 49% TBSA. Each subject had 2 comparable burn wound areas identified, excised to remove nonviable tissue, and randomized to receive StrataGraft skin tissue or autograft. Thirty subjects were enrolled with 10 subjects in Cohort 1 receiving up to 220 cm² of refrigerated StrataGraft skin tissue and 10 subjects in Cohort 2 receiving up to 440 cm² of refrigerated StrataGraft skin tissue. Ten subjects in Cohort 3 received up to 440 cm² of thawed cryopreserved StrataGraft skin tissue. None of the subjects treated with StrataGraft skin tissue exhibited any significant safety concerns and none underwent autografting prior to Day 28. Additionally, 27 of the 28 per-protocol subjects (96%) exhibited complete wound closure of StrataGraft treatment sites at Month 3. Molecular analysis of biopsies taken from treated wound sites at Month 3 demonstrated no evidence of StrataGraft skin tissue DNA, indicating that the cellular components of StrataGraft skin tissue were no longer present.

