13.3.2. Other Pre-specified Endpoint Analyses

For this study, confirmed wound closure is defined as meeting wound determinations at 2 visits:

1. First, a visit at which the clinician determined complete (100%) re-epithelialization without drainage
2. Second, an assessment at a subsequent visit that is at least 2 weeks later than the first visit and wound closure was confirmed (ie, determined again) to be completely closed

Durable wound closure is achieved when a wound is observed as remaining closed at least 3 months after complete wound closure.

The clinician may determine confirmed wound closure and durable closure either by directly observing the wound or by assessing appropriate photo-documentation that will be provided electronically by the subject weekly for the first 12 weeks and then provided every other week through to Week 24. The following endpoints will be analyzed with descriptive statistics with 95% confidence intervals:

- Proportion of subjects with confirmed wound closure without autograft placement (ie, complete re-epithelialization without drainage and subsequently verified with confirmation assessment) on or before Week 12 and supported by photo-documentation
- Proportion of subjects with confirmed wound closure without autograft (verified with confirmation assessment) at each visit and supported by photo-documentation
- Proportion of subjects without autografting who maintain durable wound closure by Week 24
- Time to confirmed wound closure without autografting (verified with confirmation assessment)
- Treatment site skin quality data: The total observed POSAS by clinician and by subject. Per site descriptive statistics will be presented separately for clinician and subject values for each of the individual POSAS items and the total POSAS score, represented as the mean score across all treatment sites and supported by photo-documentation
- Number (%) of subjects with wound infection-related events

The time to first confirmed wound closure (verified with confirmation assessment) will be analyzed by the Kaplan-Meier estimation method. The period for this analysis is calculated as (the date of having the first event – the date of Day 1 + 1). Subjects not having any event during the study will have their time censored at the last available date in the study. Kaplan-Meier estimates by StrataGraft treatment area with confirmed wound closure will be presented for the following categories: $\leq 500 \text{ cm}^2$, $> 500 \text{ cm}^2$.

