3.8.2 Other Endpoint Analyses

The other endpoints of this study are:

- **Proportion of subjects with confirmed complete wound closure of all treatment sites without autograft (i.e., complete re-epithelialization without drainage and subsequently verified with confirmation assessment) on or before Week 12, supported by photodocumentation.**

Complete wound closure is defined as 100% skin re-epithelialization in absence of drainage and without autograft placement. Successful wound closure in this study requires that complete wound closure on or before Week 12 is achieved without autograft placement and is confirmed at least 14 days following the initial observation of complete closure.

The investigator will evaluate the confirmation of complete wound closure either by direct clinician observation or by subject-provided photodocumentation.

The proportion of subject with all confirmed complete treatment site closure(s) including two-sided 95% confidence intervals based on the normal approximation to the binomial will be calculated and presented.

- **Proportion of subjects with confirmed complete wound closure of all treatment sites without autograft (verified with confirmation assessment) at each visit, supported by photodocumentation.**

The planned visits are Week 1, Week 2, Week 4, Week 8, Week 12, and Week 24. However, the subjects may show up at any visit, and number and percentage will be summarized. For each visit, the denominator of the proportion of subjects is based on the total number of subjects who provided data for the visit.

- **Proportion of subjects maintaining durable wound closure by Week 24.**

Durable wound closure by Week 24 is achieved when a subject with confirmed wound closure is observed as remaining closed at least 90 days after complete wound closure through Week 24. Two summaries will be performed: 1. Denominator is mITT population 2. The denominator will be based on subjects with confirmed wound closure of all treatment sites without autograft by Week 12. The number, percentage and two-sided 95% confidence intervals based on the normal approximation to the binomial will be calculated and presented.

- **Proportion of treatment sites with confirmed complete wound closure without autograft (i.e., complete re-epithelialization without drainage and subsequently verified with confirmation assessment) on or before Week 12 and supported by photodocumentation.**

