The treatment sites will be analyzed regardless of subject. Treatment site with confirmed wound closure requires treatment site complete closure on or before Week 12 is achieved without autograft placement and is confirmed at least 14 days following the initial observation of complete closure.

The investigator will evaluate the confirmation of complete treatment site closure either by direct clinician observation or by subject-provided photodocumentation.

The proportion of confirmed complete treatment site closure including two-sided 95% confidence intervals based on the normal approximation to the binomial will be calculated and presented.

- **Proportion of treatment sites maintaining durable wound closure by Week 24.**

The treatment sites will be analyzed regardless of subject.

Durable wound closure by Week 24 is achieved when a confirmed wound is observed as remaining closed at least 90 days after a confirmed complete wound closure through Week 24. Two summaries will be performed: 1. Denominator is all treatment sites 2. The denominator will be based on a confirmed treatment site wound closure by Week 12. The number, percentage and two-sided 95% confidence intervals based on the normal approximation to the binomial will be calculated and presented.

- **Time to first confirmed complete wound closure of all treatment sites in a subject without autograft (verified with confirmation assessment at least 14 days later).**

The event for Kaplan-Meier method will be the first occurrence of all confirmed complete wound closure without autograft in a subject (first observation of complete closure verified with a second observation of complete closure at least 14 days later). The time to first confirmed wound closure will be analyzed by the Kaplan-Meier estimation method. The period for this analysis is calculated as (the date of having the first confirmed event – the date of Day 1 + 1). Subjects not having any confirmed complete closure event during the study will have their time censored at the last available date in the study. Kaplan-Meier estimates by StrataGraft treatment area with confirmed wound closure will be presented for the following categories: $\leq 500 \text{ cm}^2$, $> 500 \text{ cm}^2$.

The Kaplan-Meier estimate will be computed to determine the median time to confirmed complete wound closure without autograft placement.

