To evaluate the effects of initial re-grafting on SG treatment sites, initial complete wound closure with or without confirmation is not required. Grafting includes allograft, xenograft and other skin substitute, and autografting, which is separately calculated. The following endpoints evaluating the combination of initial complete wound closure, confirmation of complete closure, and grafting/autografting will be summarized by SG treatment site and overall (across all treatment sites per subject):

- Summary of subjects with re-grafting on StrataGraft treatment sites

- Proportion and 95% confidence intervals of subjects who achieved initial wound closure on or before Week 12
- Proportion of subjects who achieved initial wound closure for at least one wound site without grafting on or before Week 12
- Proportion of subjects who achieved initial wound closure for at least one wound site without autograft on or before Week 12
- Proportion of subjects who achieved initial wound closure at each visit up to Week 12
- Proportion of subjects who achieved initial wound closure without grafting at each visit up to Week 12
- Proportion of subjects who achieved initial wound closure without autograft at each visit up to Week 12
- Proportion of subjects who achieved initial wound closure with grafting at each visit up to Week 12
- Proportion of subjects who achieved initial wound closure with autograft at each visit up to Week 12
- Proportion of subjects who achieved $\geq 95\%$ wound closure without autograft at each visit up to Week 12
- Proportion of treatment sites $\geq 95\%$ wound closure without autograft at each visit up to Week 12
- Proportion and 95% confidence intervals of subjects who achieved confirmed wound closure on or before Week 12
- Proportion of subjects who achieved initial confirmed wound closure at each visit up to Week 12
- Proportion of subjects who achieved initial confirmed wound closure without grafting at each visit up to Week 12
- Proportion of subjects who achieved initial confirmed wound closure without autograft at each visit up to Week 12
- Proportion of subjects who achieved initial confirmed wound closure with grafting at each visit up to Week 12
- Proportion of subjects who achieved initial confirmed wound closure with autograft at each visit up to Week 12

- Proportion of subjects with confirmed wound closure without grafting at each visit
- Proportion of subjects with confirmed wound closure without autograft at each visit

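### Closure and durability proportions get normal-approximation 95% intervals with no rule near 0% or 100%; at high closure rates these under-cover and can exceed 100%

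*SAP*

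**What the plan says.** Protocol 13.3.2 lists the closure, durability and other pre-specified endpoints and says: "The following endpoints will be analyzed with descriptive statistics with 95% confidence intervals". It names no method for proportions.

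The SAP does name one. Section 3.1 sets the general rule: "The Proportion and 95% CI of subjects will be calculated using the normal approximation to the binomial distribution". Section 3.8.2 then repeats the normal approximation in four places:

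- confirmed closure of all sites by Week 12, by subject: "The proportion of subject with all confirmed complete treatment site closure(s) including two-sided 95% confidence intervals based on the normal approximation to the binomial";
- durable closure by Week 24, by subject, summarised on two denominators, of which the second is restricted: "The denominator will be based on subjects with confirmed wound closure of all treatment sites without autograft by Week 12";
- confirmed closure by Week 12, by treatment site: "The proportion of confirmed complete treatment site closure including two-sided 95% confidence intervals based on the normal approximation to the binomial will be calculated";
- durable closure by Week 24, by treatment site.

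Other intervals take the method from 3.1. One group is closure at each visit. SAP 3.8.2 promises only a number and percentage there, but protocol 13.3.2 asks for an interval and SAP 2.2.4 reports no major modification of the protocol. The denominator varies: "For each visit, the denominator of the proportion of subjects is based on the total number of subjects who provided data for the visit". The other group is two items in the later 3.8.2 list that ask for an interval without naming a method: confirmed closure by Week 12, and "Proportion and 95% confidence intervals of subjects who achieved initial wound closure on or before Week 12".

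Neither document offers an exact, score or truncated alternative, or any rule for proportions near 0% or 100%.

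**The concern.** The Wald interval is centred on the observed proportion and takes its width from that same proportion. Near 100% the estimated standard error shrinks towards zero and the symmetric interval ignores the boundary. Three things follow: it covers the true value less often than stated, its upper limit can pass 100%, and at 0% or 100% observed its width is zero.

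The trial has no hypothesis test (SAP 3.8) and no sample-size or precision calculation (SAP 2.3). These intervals are therefore the stated uncertainty for the closure and durability proportions. Where closure is high the error runs one way: the lower limit is too high, so the worst closure rate compatible with the data looks better than it should. SAP section 1 says the analyses may enter regulatory submissions and manuscripts, where an upper limit above 100% would be an evident fault.

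The median time to closure has its own Brookmeyer-Crowley interval and is not affected.

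**Working it through.** **Inputs.** Planned enrolment is about 100 (SAP 2.3). Intervals are two-sided 95%, so z = 1.96 (SAP 3.1). The earlier closure rate comes from protocol 4.3: "27 of the 28 per-protocol subjects (96%) exhibited complete wound closure of StrataGraft treatment sites at Month 3". Thirty were enrolled in that study, so its all-enrolled rate lies between 27/30 (90%) and 29/30 (97%), depending on the two subjects left out. The true closure rate and the reduced denominators in this trial are not stated. I assume rates of 80% to 98% and denominators of 50 to 100.

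**Formulas.**
- Wald: p̂ ± 1.96·√(p̂(1−p̂)/n).
- Wilson: [p̂ + z²/2n ± z·√(p̂(1−p̂)/n + z²/4n²)] / (1 + z²/n).
- Clopper-Pearson: beta quantiles, called exact below.
- Coverage at true rate p: the sum of binomial probabilities over every count x whose interval contains p (full enumeration, no simulation).
- The Wald upper limit passes 100% when n/(n + z²) < p̂ < 1.

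**The documents' own figure.** 27/28 = 96.4%, which agrees with the stated 96%. Under the SAP's formula, √(0.9643 × 0.0357/28) = 0.0351 and 1.96 × 0.0351 = 0.0687, giving 89.6% to 103.3%. The exact interval is 81.7% to 99.9%. The two all-enrolled extremes behave the same way:
- 27/30: Wald 79.3% to 100.7%, exact 73.5% to 97.9%.
- 29/30: Wald 90.2% to 103.1%, exact 82.8% to 99.9%.

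**Coverage at n = 100 (nominal 95%).**

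| True rate | Wald | Wilson | Clopper-Pearson | Chance that Wald upper limit > 100% |
|---|---|---|---|---|
| 80% | 93.3% | 94.1% | 96.7% | under 0.1% |
| 90% | 93.2% | 93.6% | 95.6% | 0.8% |
| 95% | 87.7% | 96.6% | 98.3% | 25% |
| 96% | 90.6% | 93.6% | 96.4% | 41% |
| 97% | 80.2% | 96.9% | 98.9% | 60% |
| 98% | 86.6% | 94.9% | 98.5% | 73% |

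Coverage moves up and down with p because counts are discrete, so averages are more telling. Over 80% to 90%, Wald averages 93.7% and Wilson 95.1%. Over 93% to 98%, Wald averages 90.1% (minimum 79.7%), Wilson 95.6% (minimum 92.7%) and Clopper-Pearson 97.6%.

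**Smaller denominators.** At n = 75, Wald coverage is 80.4% at a true rate of 96% and 77.9% at 98%. At n = 50 it is 87.9% at 90%, 92.0% at 95%, 78.1% at 97% and 63.5% at 98%. In that last case the chance that all 50 close, which gives a zero-width interval, is 0.98^50 = 36%.

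**When the upper limit passes 100%.** At n = 100 the threshold is 100/103.84 = 96.3%, so 97, 98 or 99 closures. At n = 50 it is 50/53.84 = 92.9%, so 47 to 49 closures.

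**Lower limits at n = 100.**

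| Closures | Wald | Wilson | Exact | Wald − Wilson | Wald − exact |
|---|---|---|---|---|---|
| 90 | 84.1% | 82.6% | 82.4% | 1.6 | 1.7 |
| 95 | 90.7% | 88.8% | 88.7% | 1.9 | 2.0 |
| 98 | 95.3% | 93.0% | 93.0% | 2.3 | 2.3 |

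(Differences are in percentage points, taken before rounding.) At 27/28 the gap to the exact limit is 89.6 − 81.7 = 7.9 points.

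**The other end.** Confirmation needs at least 14 days, so confirmed closure at the earliest visits may be near 0%. This is an inference, since no early rate is given. At 0/100 Wald gives 0% to 0%, while the exact upper limit is 3.6%. At 1/100 the Wald lower limit is negative.

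**The case against.** The strongest reply is that the damage depends on a closure rate the documents do not support for this endpoint. The 27/28 is a per-protocol count of closure at Month 3, with no stated confirmation visit, in wounds treated with at most 220 or 440 cm². Here up to about 2000 cm² over as many as three sites may be treated, and every site must close without autograft and be confirmed. Most of these differences point to a lower rate. Below about 90% the effect at n = 100 is small: Wald coverage averages 94.1% over 70% to 85%, and an upper limit above 100% is very unlikely. This stands, and it is why the finding is conditional on high closure. It does not justify a plan that has no rule if closure proves high, as the only rate cited would suggest.

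Four narrower points:

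- *Normal approximation need not mean Wald*, since a score interval also rests on one. True, but Wald is the ordinary reading and the SAP names no score method. If one was meant, the text still needs to say so.
- *The per-visit intervals are inferred.* They are, from protocol 13.3.2 together with the rule in SAP 3.1.
- *Site-level coverage is not as tabulated.* Sites are pooled regardless of subject, so counts may exceed 100 and outcomes within a subject may be correlated. The coverages above assume independent subjects and do not carry over. Clustering is a separate matter that a change of interval does not resolve.
- *Nothing turns on these intervals.* No test, sample-size target or primary analysis uses them, and readers can recompute them from the counts. This limits how serious the point is, not whether it is right.

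**Conclusion.** The concern holds. The SAP fixes a normal-approximation interval for the closure and durability proportions and gives no boundary rule. If true closure is about 93% to 98% with 100 subjects, the nominal 95% interval covers about 90% of the time on average and as little as 80%. For 90 to 98 observed closures its lower limit is about 2 percentage points too high, against Wilson as well as exact limits. At a rate of 90% the shortfall is modest, and between 80% and 90% it is mild. Restricted or per-visit denominators make matters worse.

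This rests on three assumptions: the Wald reading, independent subjects, and a closure rate in the upper range, which the Phase 1b result makes plausible but the documents do not state for this trial. The effect is on reported precision only; point estimates and the primary safety endpoint are untouched. It should be corrected, but it does not threaten the trial's main conclusion.

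**What to change.** Name one interval that behaves near the boundary: Wilson, or Clopper-Pearson if guaranteed coverage is preferred. State it once in SAP 3.1 and at each of the four places in 3.8.2 that now specify the normal approximation. The per-visit intervals and the two later 3.8.2 items that ask for a CI then take it from 3.1.

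The cost is five wording edits and one option in the proportion program, with no new data and no conflict with the protocol, which names no method. The intervals become asymmetric and, near the boundary, somewhat wider below the estimate; Clopper-Pearson is conservative (97.6% average coverage over 93% to 98% at n = 100). The edit belongs in the SAP before database lock, because a change of method after the results are seen would be post hoc.
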